4.4 Other Modalities or Procedures

Fluorescence-guided resection will be performed using the standard surgical operating

microscope. The surgical operating microscope will be adapted with a filter set intended to visualize fluorescence excitation in the wavelength range from 390nm to 440nm and for observation in the 600-700nm range. The adaptation includes standard white light emission source and a combination of excitation and observation low and high pass optical filters with slightly overlapping transmission integrated into their optical configuration. The proposed filter set is commercially available globally. A small fraction of excitation light is remitted from the tissue, which then generates a blue tone contrast from the healthy brain anatomy in contrast to the bright red. 5-ALA induced PPIX fluorescence. Thus, there are two light sources to illuminate the resected field: White light phase and Blue light phase. During the white light illumination, an attenuator reduces irradiance to approximately 50% to minimize the need for illumination adjustment. During the blue light phase, an electromagnetic filter switch is used to introduce a dielectrically coated observation filter with a 600-700nm wavelength into the light paths of the surgical microscope. These filters transmit tumor associated red PPIX fluorescence and a portion of backscattered normal tissue blue excitation light which does not fluoresce. A camera system on the microscope is used to record 5-ALA/PPIX red fluorescence.

Gleolan® (5-ALA) will be reconstituted in the minimum volume of sterile water and may be mixed with a clear liquid or apple fruit juice before being given orally approximately 3 hours (3-5h) prior to scheduled surgery. Image-guided microsurgical resection of the tumor will be undertaken as per operator preference. Following standard surgical entry, further tumor resection will be performed by switching to the microscope fluorescence 'blue light' mode.

Photographs will be taken during the 'blue light' imaging to provide identification of optical fluorescent tumor. Images will be taken before, during and after resection to capture tumor fluorescence. All tumor specimens will be sent to pathology for frozen examination as per institutional standard of care. Any tissue specimens from the fluorescent areas will be photographed and sent for permanent histopathologic examination and molecular genetic analysis to confirm the presence of malignant tumor. The intraoperative pictures of the resection cavity in the 'blue light' mode will be analyzed to provide confirmation of tissue/tumor fluorescence associated with tumor resection. The surgeon will document whether visualization of fluorescence was present with each of the labeled tissue specimens. The remainder of the resection will be performed with the ability to switch between white light and blue light as chose by the surgeon. If no fluorescence is observed in the resection site it will be noted, but will otherwise undergo identical tumor resection, photography and histopathologic examination.

Pathologic confirmation of tumor type will be made by a pathologist who will not be informed of the fluorescence status of the tissue samples. Histopathology will characterize the resected tissue as

- (1) Diagnostic tissue or not
- (2) Presence of malignant tumor cells
- (3) Pathologic grading and tumor type

Genetic testing will be performed in accordance with standard of care at the testing institution for the tumor specimens.

4.5 **Duration of Therapy**

One-time, single dose administration of oral Gleolan®(5-ALA) (20mg/kg) is planned 3-5h prior to induction of anesthesia. However, surgery can be initiated up to 8 hours after dosing. In the event of allergic reaction, other severe adverse effect, or changes in the patient's condition prior to surgery rendering the patient unacceptable for further treatment in the judgement of the investigator, or patient decides to withdraw from the study, the therapy protocol will be ended and fluorescent-guided surgery will not proceed.

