The oral solution is intended for single (partial) use. 5-aminolevulinic acid hydrochloride is administered orally to adult patients with head and neck malignancy prior to tumor removal by surgery. 5- Aminolevulinic acid is a prodrug that is metabolized intracellularly to form the fluorescent molecule protoporphyrin (PPIX), which is selectively accumulated in tumor cells and epithelial tissue. Following excitation with blue light (λ = 400 – 410 nm) the PPIX, which has accumulated selectively in the malignant tissue, the tumor emits a red-violet light (red-light fluorescence). Tumor resection is extended as the surgeon is able to identify malignant tissue as differentiated from normal tissue after administration of 5-aminolevulinic acid (Stummer et al. 2006, 2010).

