8.0 STATISTICAL CONSIDERATIONS

8.1 Study Design/Study Endpoints

This is a single center, single arm pilot study conducted at the Mount Sinai Health System with 23 subjects planned for enrollment. The aim is to examine feasibility of 5-ALA (Gleolan®) use as an adjunct diagnostic imaging tool to detect malignant tumor tissue in head and neck and skull base cancer patients. Eligible patients will take 5-ALA 3h prior to surgery with single oral dose of 20mg/kg. The standard surgical procedure will be conducted accompanied by the intra-operative blue light microscopic image for surgeons to assign PPIX tissue fluorescence scores of no brightness (0), mild brightness (1-pink), moderate brightness (2-orange) or robust brightness (3- lava-like orange). The resected tissues will be examined by pathologists to confirm presence of cancer cells.

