8.2 Sample Size and Accrual

There is no previous publication for applying 5-ALA to head and neck cancer patients. The sample size calculation is based on the experience of 5-ALA in brain cancer. A literature review study summarized the usage of 5-ALA in patients with malignant Gliomas between 2000 and 2015.3 The sample sizes in the studies included in the review ranged from 11 to 97. The sensitivity ranged from 75% and 95% while the specificity ranged from 53% to 96%. In our study, all tissue samples will be collected from the head and neck cancer patients undergoing standard of care surgical resection. The surgeons will provide the pathologists with the patient resected specimen marked, typically in 4 different regions with 3 regions located within the tumor region and 1 located at the boundary or outer region of the tumor. Each region will be marked according to the associated intensity of the PPIX tissue fluorescence score at that location as no brightness (0), mild brightness (1-pink), moderate brightness (2-orange) or robust brightness (3- lava-like orange). Thus each patient is expected to contribute 1 tissue sample from a normal margin region and 3 tissue samples from the tumor tissue region at a ratio of 1:3 (i.e. the pathologists will examine the samples from each patient histopathologically), which translates to a tumor tissue prevalence of 75% in the overall tissue samples.

The following calculations were performed using PASS 15 Power Analysis and Sample Size Software (2015). NCSS, LLC. Kaysville, Utah, USA, ncss.com/software/pass and using the methods for calculating sample size for co-primary endpoints of sensitivity and specificity.⁴¹⁻⁴³

Assuming a prevalence of 75% and a sample sensitivity of 85%, the sample size needed to estimate a two-sided 95% sensitivity confidence interval with a width of at most 35% (\pm 17.5% precision assuming asymptotic with continuity correction method) is at least 23.We will use a sample size of 23 in this study.

If the prevalence is as low as 50% in our sample then the width of our 75% sensitivity confidence interval will increase to 40.6% (± 20.3 precision) which still gives a lower bound for the CI above 50%.

The sample size calculation is performed conservatively assuming only 1 measure per patient, but there will be typically 4 per patient which will improve precision of estimates.

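### Section 4.4 lets resection continue under blue light while 8.1 and 8.2 describe standard surgery with fluorescence scored, and nothing keeps tissue taken because it fluoresced out of the primary sensitivity table

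*Combined protocol and SAP*

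**What the plan says.** Section 4.4 describes an operation in which fluorescence has a working role. It states "Fluorescence-guided resection will be performed using the standard surgical operating" microscope, and then "Following standard surgical entry, further tumor resection will be performed by switching to the microscope fluorescence" mode. Later it adds: "The remainder of the resection will be performed with the ability to switch between white light and blue light as chose by the surgeon". On tissue handling it says: "Any tissue specimens from the fluorescent areas will be photographed and sent for permanent histopathologic examination". For a resection site that shows no fluorescence, it says the site "will otherwise undergo identical tumor resection, photography and histopathologic examination". The pathologist is not told the fluorescence status.

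Section 8 describes the operation differently. Section 8.1 says: "The standard surgical procedure will be conducted accompanied by the intra-operative blue light microscopic image for surgeons to assign PPIX tissue fluorescence scores". Section 8.2 takes all samples from "patients undergoing standard of care surgical resection". It has the surgeon mark typically four regions on the resected specimen, three within the tumor and one at its boundary or outer part, each with its fluorescence score. The assumed tumor prevalence of 75% comes from that three-to-one mix.

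Section 8.3 defines sensitivity as the share of tumor tissues that test positive (score 1 or more) and fits a GEE model to the multiple samples from each patient. It does not restrict which samples enter.

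**The concern.** The two descriptions differ on whether fluorescence only accompanies the operation or also steers it. Neither says whether tissue beyond what white light alone would have led the surgeon to take may be removed and sampled because it fluoresces. Neither says that sampling sites are fixed by location before blue light is used. The word typically in 8.2 leaves room for samples outside the three-plus-one frame.

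This matters because fluorescence is the index test. A sample that exists because it fluoresced cannot be a false negative or a true negative. If pathology finds it malignant, it adds one to both numerator and denominator of sensitivity. If pathology finds it benign, it adds one to the denominator of specificity only. Both effects are systematic. The GEE model allows for correlation within a patient but not for selection on the test result, and blinding the pathologist does not help because selection comes before pathology.

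**Working it through.** **Inputs.** 23 patients, three tumor samples and one boundary sample each, expected to be normal (8.2). This gives 23 × 3 = 69 tumor samples and 23 × 1 = 23 benign samples. Assumed sensitivity is 85%, assumed prevalence 75%, and the cited glioma ranges are 75–95% for sensitivity and 53–96% for specificity (all 8.2). The number of samples added because of fluorescence is not in the documents, so it is varied below.

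**The plan's own figure.** The interval is p ± [1.96 × √(p(1−p)/n) + 1/(2n)], with the upper limit cut at 1. With p = 0.85 and n = 17 tumor units, the half-width is 0.170 + 0.029 = 0.199, so the interval runs from 0.651 to 1.000, a width of 0.349. Then 17/0.75 = 22.7, rounded up to 23. The stated sample size reproduces, and this point does not alter it.

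**Sensitivity with m added malignant samples, all test-positive.** Apparent sensitivity = (69 × s + m)/(69 + m). This pools samples with equal weight.

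| True s | m = 6 | m = 12 | m = 23 |
|---|---|---|---|
| 0.75 | 57.75/75 = 0.770 | 63.75/81 = 0.787 | 74.75/92 = 0.8125 |
| 0.85 | 64.65/75 = 0.862 | 70.65/81 = 0.872 | 81.65/92 = 0.8875 |

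These values of m run from about one added sample for every four patients (6/23 = 0.26) to one for every patient. The upward shift is 2 to 6 points at a true 75% and 1 to 4 points at a true 85%.

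**Specificity with k added benign samples, all test-positive.** Apparent specificity = 23 × Sp/(23 + k). With k = 3:

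- Sp = 0.53: 12.19/26 = 0.469
- Sp = 0.75: 17.25/26 = 0.663
- Sp = 0.96: 22.08/26 = 0.849

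Specificity moves more per added sample because its planned denominator is 23 rather than 69.

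**The case against.** The strongest reply is that the sections can be read together. Section 8.1 does not say fluorescence is only observed, and 4.4 leaves the microsurgical technique to the operator's preference. If the three-plus-one regions are chosen by location on a specimen whose extent was set under white light, little or no bias arises. That is a fair reading, but no section states it. The instruction to continue in blue-light mode and the surgeon's free choice of light point the other way, so the ambiguity stands.

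The sentence in 4.1, "Tumor resection is extended as the surgeon is able to identify malignant tissue as differentiated from normal tissue", should carry no weight here. It is product background that cites earlier published work, not an operating instruction. The point rests on 4.4 alone.

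A reader might infer a stronger bias: that non-fluorescent tumor is left in the patient, so false negatives vanish. If a share r of such tumor went unsampled, apparent sensitivity would be s/(s + (1−s)(1−r)), and a true 85% would read 88% at r = 25% and 92% at r = 50%. The documents do not support this. No passage permits leaving tumor because it does not fluoresce. Section 4.4 promises the same resection and histology for a site without fluorescence, although it does not expressly cover mixed sites. Applying r to every tumor sample also ignores that three of the four regions lie within the tumor.

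A reader might also infer that removal of benign fluorescent tissue would go unseen. It would not: such samples count as false positives in specificity and PPV, margins are recorded (5.2.2), and adverse events are recorded whether or not drug-related (6.2.1). Extent of resection is not an endpoint, but in a 23-patient feasibility pilot that is a design preference rather than an error.

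**Conclusion.** The concern holds in a limited form. Section 4.4 and sections 8.1–8.2 must be reconciled on whether fluorescence may change the extent of resection. As written, samples selected by a positive test can enter the primary table. Under the assumed 6 to 23 added malignant samples, sensitivity would read 1 to 6 points too high. Three added benign samples would lower specificity by about 6 to 11 points across the plan's cited range. The sensitivity shift is well inside the stated precision of ±17.5 points, but it runs in one direction and the reported interval would not reflect it.

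These sizes rest on the assumed number of added samples, on equal weighting, and on the three-plus-one frame otherwise being kept. If no sample is taken because it fluoresced, the bias is zero. The documents give no basis for claiming larger inflation through tumor left behind. This is an inexpensive improvement to the plan, not a flaw that invalidates the design.

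**What to change.** First, align 4.4, 8.1 and 8.2 on whether fluorescence may change the extent of resection. That is a clinical decision for the sponsor, and the statistical remedy works under either answer.

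Second, add one case report form field per sample, completed in the operating room: the sample belongs to the three-plus-one frame and was chosen by location regardless of fluorescence, or it was taken or added because of fluorescence. State in 8.3 that primary sensitivity and specificity use the first group, and tabulate the second group separately by score and pathology.

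The cost is a wording change, one field, and the surgeon's effort to record the reason for each sample at the time, since it cannot be reliably reconstructed later. The surgeon who records it knows the fluorescence result, so the selection rule for frame samples should be written down beforehand. A few samples leave the primary table, and the planned 23 patients are unaffected. The flag cannot correct for tumor that was never resected.

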4.6 Duration of Follow Up

Analysis of progression and correlative studies will be performed as per standard of care for 6 weeks post-surgery. Follow-up will consist of 3 time points: within 48h post-surgery, a 2 week and a 6 week postoperative office visit. Patients removed from treatment for unacceptable adverse events will be followed until resolution or stabilization of the adverse event.

4.7 Removal of Patients from Protocol Therapy

Patients will be removed from therapy when any of the criteria listed in Section 5.5 apply. Notify the Principal Investigator, and document the reason for study removal and the date the patient was removed in the Case Report Form. The patient should be followed-up per protocol.

4.8 Patient Replacement

Patients who withdraw from the study will be replaced through further recruitment at clinical sites to meet target recruitment goals.

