2.0 STUDY OBJECTIVES

2.1 Primary Objectives

2.1.1 To assess the feasibility of using oral Gleolan® as an adjunct diagnostic imaging tool for malignant tumor tissue fluorescence in a pilot cohort of head and neck and skull base cancer patients.

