2.3 Endpoints

2.3.1 Definition:

Safety: Gleolan®-related adverse events will be recorded using standardized toxicity criteria and known side effect profile up to 6 weeks after surgery. Monitoring for adverse events will take place before and after Gleolan® administration, 48h after surgery, 2 weeks and 6 weeks postoperatively.

2.3.1 Primary endpoint:

The feasibility of using oral Gleolan® as an adjunct diagnostic imaging tool for malignant tumor tissue fluorescence will be primarily assessed by computing sensitivity of intraoperative Gleolan® induced PPIX tissue fluorescence.

PPIX tissue fluorescence will be defined categorically as "no" (score 0), "low" (score 1), "medium" (score 2), and "high" (score 3) by operative surgeon, and images will be recorded. For purposes of computing measures of diagnostic performance a score of 0 will be considered a negative test result and a score of 1, 2 or 3 will be considered a positive test result.

2.3.2 Secondary endpoints:

2.3.2.1 The diagnostic performance of Gleolan® will further be assessed by computing measures of specificity, positive predictive value (PPV), negative predictive value (NPV), and accuracy of intraoperative Gleolan® induced fluorescence with a score of 0 will be considered a negative test result and a score of 1, 2 or 3 will be considered a positive test result.

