We will continuously monitor the rate of sustained Grade 3 or 4 elevations in LFTs at 6 weeks following Gleolan® administration and accrual will be halted if there is sufficient evidence that the sustained Grade 3 or 4 LFT elevation rate exceeds the acceptable rate of 5% by more than 5% (unacceptable rate 10%). If the cumulative number of patients that experience grade 3 or 4 elevations in the LFTs at 6 weeks from drug administration is greater than the associated boundary value $b_{\mbox{\tiny K}}$ listed in the table below, among the k patients enrolled in the trial, enrollment in the trial will be halted for safety considerations prompting IRB notification and a DSMB meeting will be requested.

# of accrued	2-9	10-20	21-23
subjects, k			
Boundary, b _k	1	2	3

The following table shows the probability of early stopping if the true rates of sustained grade 3 or 4 elevations in the LFTs are at or lower than 10%. For safety of the participants, we would like to have a low probability of early stopping if the sustained LFT rates are low, but high probability of early stopping if the sustained LFT rate is high.

Probability of early stop based on true grade 3 or 4 LFT rate					
True SAE rate	5%	6.2%	7.5%	8.8%	10%
Probability of early stop	0.15	0.21	0.28	0.36	0.44

This stopping rule was computed using the toxbdry function in R and calculations of this function are based on methods described in Chapter 12 of Jennison and Turnbull³⁹ and in the illustrative paper by Ivanova, Qaquish and Schell⁴⁰.

toxbdry(0.05,0.10,c(1:23),cP0=0.15,cP1=0.30,ngrid=5)

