8.3 Data Analyses Plans

The characteristics of participants and information collected before 5-ALA is administered will be summarized using standard statistics, such as mean, SD, median, 1st and 3rd quartiles for continuous variables, and count, percentage for categorical variables.

Analysis of the primary endpoint

To assess the feasibility of using 5-ALA as an adjunct diagnostic imaging tool to detect malignant tumor tissue, the point estimate of sensitivity will be computed according to the following definition:

Sensitivity: proportion of tumor tissues that tested positive on 5-ALA induced fluorescence.

The definition of a positive test is the fluorescence score equal to or greater than 1 while a negative test is considered a score of 0. For the assessment of sensitivity and

specificity, histological diagnoses of any upper aerodigestive head and neck cancer in addition to squamous cell carcinoma, carcinoma in situ, and severe and moderate dysplasia were classified as malignant, whereas light dysplasia and normal tissue will be classified as benign by pathologists. The analysis population includes all patients who sign the inform consent regardless of taking 5-ALA or not. Each patient is expected to contribute multiple samples and the pathologists will determine presence of malignancy in each sample. A contiguous table (fluorescence scores vs. pathological results) that presents the frequency and percentage of each cell will be prepared. A generalized estimating equation (GEE) model accounting for repeated measure within each patient will be used to estimate the sensitivity and specificity.⁴⁴⁻⁴⁵ For sensitivity and specificity, the dependent variable is the PPIX fluorescence test result (positive vs. negative) and the independent variable is presence of tumor cells (tumor vs. normal).

Analysis of the secondary endpoints

To further determine the diagnostic performance of 5-ALA for detecting of malignant tumor tissue, specificity, PPV and NPV will be computed. Specificity will be computed according to the following definition:

Specificity: proportion of normal tissues that tested negative on 5-ALA induced fluorescence.

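### Replacement is uncapped while the liver boundary counts enrolled patients and ends at 23, and the feasibility objective has no patient-level completion measure

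*Combined protocol and SAP*

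**What the plan says.** The primary objective in Section 2.1 is "To assess the feasibility of using oral Gleolan® as an adjunct diagnostic imaging tool for malignant tumor tissue fluorescence". Section 2.3 says this "will be primarily assessed by computing sensitivity of intraoperative Gleolan® induced PPIX tissue fluorescence". Section 8.3 makes the tissue sample the unit: "Sensitivity: proportion of tumor tissues that tested positive on 5-ALA induced fluorescence". The secondary endpoints are specificity, predictive values, accuracy and related adverse events. None counts patients who were dosed, operated on under blue light, or gave a scored specimen.

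Section 8.1 plans the study "with 23 subjects planned for enrollment". Section 8.3 then says: "The analysis population includes all patients who sign the inform consent regardless of taking 5-ALA or not". Section 4.8 adds: "Patients who withdraw from the study will be replaced through further recruitment at clinical sites to meet target recruitment goals".

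Section 4.5 foresees patients stopping before surgery because of an allergic reaction, another severe adverse effect, a change in condition or their own decision to withdraw. In those cases "the therapy protocol will be ended and fluorescent-guided surgery will not proceed". Section 4.2 keeps every treated patient evaluable for toxicity, and Section 5.5 has reasons for discontinuation documented.

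Section 6.5 compares the cumulative number of patients with grade 3 or 4 liver-test elevations at six weeks with a boundary value, "among the k patients enrolled in the trial, enrollment in the trial will be halted". The table heads its columns by accrued subjects: 1 for k = 2 to 9, 2 for k = 10 to 20, and 3 for k = 21 to 23. The software call also ends at 23.

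**The concern.** Two parts of the plan do not fit the replacement rule.

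**The safety boundary.** A replaced patient is at least the 24th enrolled by the end of accrual, and there is no boundary value for k above 23. An enrolled patient who never takes the drug cannot have a drug-related event, yet still advances k. The allowed number of events then rises faster than exposure does, so the rule is looser than its table of stopping probabilities implies.

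**The feasibility answer.** A patient who is dosed but has no scored specimen adds nothing to the numerator or the denominator of sensitivity. The all-consented population keeps that patient in name, but no rule says how such a patient is handled. The analysis population, the replacement rule and the sample-level estimator have not been reconciled. At stake is whether the report shows how often the procedure could be carried through in dosed patients, which is part of any feasibility question.

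**Working it through.** **Inputs.** From Section 6.5: the boundary above, halting when the count exceeds b_k, an acceptable rate of 5% and an unacceptable rate of 10%. From Sections 8.1 and 8.2: N = 23, sensitivity 85%, prevalence 75%. The number of withdrawals is not given; four is used as an illustration.

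**Origin of 23.** With n = 0.75 × 23 = 17.25 tumor samples, the continuity-corrected half-width is 1.96 × √(0.85 × 0.15 / 17.25) + 1/(2 × 17.25) = 0.169 + 0.029 = 0.198. The interval is 0.652 to 1 (truncated), a width of 0.348. N = 22 gives 0.353, so 23 is reproduced. It contains no allowance for patients who give no specimen.

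**Method for the boundary.** Let f_k(x) be the probability of still being open after k patients with x events. For a dosed patient, f_k(x) = (1 − p) f_{k−1}(x) + p f_{k−1}(x − 1), kept only where x ≤ b_k. For an undosed patient, f_k(x) = f_{k−1}(x), under the same limit. P(stop) = 1 − Σ f_N(x).

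**The plan's own figures.** With all 23 dosed, the printed table gives 0.11 at a true 5% rate and 0.38 at 10%. Section 6.5 states 0.15 and 0.44. Adding an unprinted b_1 = 0 gives 0.14 and 0.41. The stated probabilities therefore do not follow exactly from the printed table. The comparisons below all use the printed table, so they are on one footing.

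**Four replaced patients.** In each replacement row, 27 are enrolled.

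| Scenario | Dosed | P(stop), true 5% | P(stop), true 10% |
|---|---|---|---|
| No replacement, all dosed | 23 | 0.11 | 0.38 |
| Four undosed enrolled first, no value past k = 23 | 23 | 0.06 | 0.24 |
| Same, last value (3) carried to k = 27 | 23 | 0.06 | 0.28 |
| Four undosed at k = 20 to 23, no value past 23 | 23 | 0.10 | 0.35 |
| Four dosed and then withdrawn, last value carried to k = 27 | 27 | 0.12 | 0.42 |

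In the second row only 19 dosed patients (k = 5 to 23) are ever compared with a boundary, each at a value meant for four more exposed patients. Order matters: undosed patients early do most harm, and the same four placed last cost about three points. Carrying 3 forward serves only to size the gap and is not a proposed boundary.

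**Completion.** Suppose 23 patients complete and w dosed patients fail and are replaced. The completion proportion is 23/(23 + w), with exact (Clopper-Pearson) 95% intervals:

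| w | Proportion | 95% interval |
|---|---|---|
| 2 | 23/25 = 92% | 74% to 99% |
| 4 | 23/27 = 85% | 66% to 96% |
| 6 | 23/29 = 79% | 60% to 92% |
| 8 | 23/31 = 74% | 55% to 88% |

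The sensitivity computed from the 23 completers is the same in all four rows.

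**The case against.** The strongest reply is that the plan already holds on to these patients. Section 8.3 analyses everyone who consents, Section 4.2 keeps every treated patient in the toxicity set, related adverse events are an endpoint, and removal reasons are documented. A reader might infer that replaced patients vanish without trace; the documents do not support that. What stands is narrower: they cannot move a per-sample sensitivity, and no analysis in Section 8.3 uses the recorded reasons.

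A reader might also infer that every failed procedure is replaced. Section 4.8 speaks of patients who withdraw. Section 4.5 lists allergic reaction, severe adverse effect and change in condition separately from the patient's own decision, and whether Section 4.8 reaches those cases is unclear. Emesis is not such a case unless the patient also withdraws. Section 4.1.2 only rules out a repeat dose, and under Section 4.4 a site without fluorescence is still resected and examined. Tumor tissue there would score 0 and lower sensitivity.

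Nor do the documents support saying that the trial would reach the same feasibility conclusion whatever the failure count, because they set no success threshold. Assessing feasibility primarily by sensitivity is a disclosed choice in a pilot sized for precision, and the lack of a completion rate does not bias that estimate.

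On safety, passing 23 dosed patients requires withdrawal after dosing, and the effect is then small. Section 6.5 also states its halting principle in general terms, and part of the monitoring text in Section 9 was not in the copy read, so no absence of other oversight is claimed. These points limit the size of the concern. They do not supply a boundary value past 23 or stop undosed patients from advancing k.

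**Conclusion.** The point holds as a moderate one, in two parts.

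First, read literally, Sections 4.8 and 6.5 do not work together. Any replacement takes the enrolled count past the last defined boundary, and undosed enrolled patients loosen the rule. With four undosed patients, the probability of stopping at a true 10% rate falls from 0.38 to between 0.24 (enrolled first) and 0.35 (enrolled at k = 20 to 23) when nothing is defined past 23. If every replaced patient was dosed, the change is only from 0.38 at 23 to 0.42 at 27 with the last value carried on.

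Second, the feasibility objective lacks a patient-level measure, so completion anywhere from 92% to 74% in the illustration would leave the reported sensitivity unchanged.

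This rests on k counting all enrolled patients, dosed or not, as the wording of Section 6.5 suggests. It also assumes independent events with a constant rate, each six-week result known as soon as the patient is counted, and six-week tests obtained from patients withdrawn after dosing. The numbers of withdrawals are assumptions chosen to show a range and are not forecasts.

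**What to change.** - **Section 6.5:** define k as patients dosed, and compute boundary values past 23 by the same method to cover replacements. Recheck the stated stopping probabilities against the printed table at the same time.
- **Section 4.8:** state whether replacement covers patients stopped by the investigator as well as those who withdraw themselves, and whether it applies before dosing, after dosing or both.
- **Sections 2.3 and 8.3:** keep sensitivity as primary. Add a supporting feasibility measure: patients with at least one scored region paired with histology, divided by all patients dosed, with an exact 95% interval and reasons for failure. Give the counts consented, dosed, operated on under blue light and scored. State that replaced dosed patients stay in this denominator, and say how it relates to the all-consented population.

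Section 4.2 needs no change, since it already keeps dosed, replaced patients in the toxicity set. The cost is protocol wording, a rerun of the boundary calculation and one table. Removal reasons are already documented under Section 5.5, and no added procedures are needed. The downside is that the feasibility result may look less favourable.
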